Best overall response (BOR) is defined for each study participant as the best overall tumor response from each tumor assessment (scheduled and unscheduled assessments performed between Days 21 and 28 of every even cycle of study treatment) according to the RECIST criteria for changes in target and non-target lesions and the appearance of new lesions. Best overall response is determined from the start of study treatment until documented objective disease progression or the date of subsequent anti-cancer therapy (systemic therapy, surgery or radiotherapy for cancer), whichever occurs first. If anti-cancer therapy is started on the same day as a tumor assessment, then the overall response from that assessment will be used in the derivation of BOR. For a BOR of SD, a participant's tumor measurements must have met the SD criteria at least once after the start of study treatment at a minimum interval of no less than 6–8 weeks (42–56 days).

For Part A of this study, BOR determination requires confirmation of CR or PR responses at a subsequent assessment ≥ 4 weeks (28 days) after the criteria for CR or PR responses are first met. In addition, Table C in Appendix 10.9 of the protocol provides the derivation of BOR when confirmation of CR and PR responses are required. Confirmed BOR and unconfirmed BOR will be derived programmatically based on the overall tumor assessment data recorded on the eCRF

by the investigator and using the detailed guidance included in the Derivation of Efficacy Endpoints document Version 0.6 (dated 21 January 2022).

Duration of response (DOR) will be calculated for participants with a confirmed BOR of CR or PR as the time in days from the start date of the confirmed CR or PR to the first date that recurrent or progressive disease is objectively documented (i.e. according to the RECIST guidelines). This will be referred to as the duration of confirmed response and the following calculation will be performed:

$$\begin{aligned} & \text{Duration of Confirmed Response} \\ & = (\text{Date of First Objective Disease Progression} \\ & \quad - \text{Start Date of Confirmed CR or PR Response}) + 1 \end{aligned}$$

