For participants who die without objective disease progression, duration of confirmed response and duration of unconfirmed response will be censored on the date of death, regardless of cause. For a participant who discontinues early from Part A of the study with no objective disease progression, duration of confirmed response and duration of unconfirmed response will be censored on the date of their last available (scheduled or unscheduled) tumor assessment at which a lack of objective disease progression was determined. Participants who discontinue study treatment but who do not have documented objective disease progression (i.e. according to the RECIST guidelines), duration of confirmed response and duration of unconfirmed response will be censored at the date of their last available (scheduled or unscheduled) tumor assessment

at which a lack of objective disease progression was determined. Such participants might include those that are ongoing in Part A at the time of any defined data cut-off.

In the sensitivity analyses of duration of confirmed response and duration of unconfirmed response, the same censoring rules will apply except that the date of last contact will be used for the censoring of participants who discontinue early from Part A, complete Part A of the study or are ongoing in the study at a data cut-off for Part A without objective disease progression, clinical disease progression or death.

Date of last contact will be the latest of the dates of premature study termination and of last contact recorded on Study Termination eCRF page, the date of death, the date of last dose of study treatment, the dates of all visits, AE start and end dates (with partial dates imputed as earliest possible) and the date of contact recorded on the Survival Safety Follow-up and Survival Final Follow-up eCRF forms.

Further details on the derivation of duration of confirmed response and duration of unconfirmed response are included in the Derivation of Efficacy Endpoints document Version 0.6 (dated 21 January 2022).

Progression-free survival (PFS) will be calculated as the time in days from the first dose of study treatment to the date of the first documented objective disease progression (i.e. according to the RECIST guidelines), or death due to any cause, whichever occurs first. The following calculation will be performed:

$$PFS = (Date\ of\ Objective\ Progressive\ Disease/Death - Date\ of\ First\ Dose) + 1$$

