Participants who die due to any cause without a documented objective disease progression will be considered to have progressed on the date of their death. Participants who do not have any post-Baseline tumor assessments will be censored on the date of their first dose of study treatment. Participants who discontinue early from Part A or discontinue study treatment without documented objective disease progression or death, will be censored on the date of their last available (scheduled or unscheduled) tumor assessment at which a lack of objective disease progression was determined. Participants who start anti-cancer therapy during Part A without a prior documented objective disease progression will be censored on the date of their last available (scheduled or unscheduled) tumor assessment prior to the initiation of the subsequent anti-cancer therapy. If anti-cancer therapy starts on the same date as the participant's tumor assessment and determination of objective disease progression, or the participant's death (due to any cause), then the participant will not be censored and the participant will be included as having an uncensored event on this date. This censoring rule will also be applied to participants who are ongoing at any data cut-off for an analysis of Part A data who have no documented objective disease progression. The use of anti-cancer therapy during Part A will be identified via ongoing medical review of the concomitant medications together with the start dates of further anti-cancer therapy information recorded on the survival follow-up pages of the eCRF.

As a sensitivity analysis, PFS will also be calculated as the time in days from the first dose of study treatment to the date of the first documented objective disease progression (per RECIST 1.1), the date of clinical disease progression, as determined by the investigator, or the date of death due to any cause, whichever occurs first. Last contact date (as defined above for DOR) will be used for the censoring of participants still alive with no reported disease progression

(objective or clinical). The same rules described above for the censoring of participants who start anti-cancer therapy will be applied in this sensitivity analysis.

Further details on the derivation of PFS are included in the Derivation of Efficacy Endpoints document Version 0.6 (dated 21 January 2022).

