For participants who die without objective disease progression, duration of confirmed response and duration of unconfirmed response will be censored on the date of death, regardless of cause. For a participant who discontinues early from Part A1 of the study with no objective disease progression, DOR will be censored on the date of their last available (scheduled or unscheduled) tumor assessment at which a lack of objective disease progression was determined. Participants who discontinue study treatment but who do not have documented objective disease progression (i.e. according to the RECIST guidelines), duration of confirmed response and duration of unconfirmed response will be censored at the date of their last available (scheduled or unscheduled) tumor assessment at which a lack of objective disease progression was determined. Such participants might include those that are ongoing in Part A1 at the time of any defined data cut-off. Likewise, participants who have not discontinued early and do not have documented objective disease progression after a confirmed or unconfirmed response, duration of confirmed response and duration of unconfirmed response will be censored at the date of their last available (scheduled or unscheduled) tumor assessment.

In the sensitivity analyses of duration of confirmed response and duration of unconfirmed response, the same censoring rules will apply except that the date of last contact will be used for the censoring of participants who discontinue early from Part A1 without objective disease progression, clinical disease progression or death.

Date of last contact will be the latest of the dates of premature study termination and of last contact recorded on Study Termination eCRF page, the date of death, the date of last dose of study treatment, the dates of all visits, AE start and end dates (with partial dates imputed as earliest possible) and the date of contact recorded on the Survival Safety Follow-up and Survival Final Follow-up eCRF forms.

Further details on the rules to apply in the derivation of duration of confirmed response and duration of unconfirmed response are included in the Derivation of Efficacy Endpoints document Version 0.6 (dated 21 JAN 2022) which has been developed to support this SAP.

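### The SAP's DOR rules have no cut-off at subsequent anti-cancer therapy, although BOR and PFS in the same section do

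*SAP*

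**What the plan says.** All three definitions stand in Section 10.1.1 of the Part A SAP and, with small differences, in Section 10.1.1 of the Part A1 SAP.

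- **BOR** is collected "until documented objective disease progression or the date of subsequent anti-cancer therapy (systemic therapy, surgery or radiotherapy for cancer), whichever occurs first".
- **PFS**: participants who start another anti-cancer therapy with no earlier objective progression "will be censored on the date of their last available (scheduled or unscheduled) tumor assessment prior to the initiation of the subsequent anti-cancer therapy". A same-day provision keeps progression or death on the therapy start date as an event. For the PFS sensitivity analysis the SAP adds: "The same rules described above for the censoring of participants who start anti-cancer therapy will be applied in this sensitivity analysis".
- **DOR** runs from the start of response "to the first date that recurrent or progressive disease is objectively documented (i.e. according to the RECIST guidelines". For participants who stop study treatment without objective progression, "duration of confirmed response and duration of unconfirmed response will be censored at the date of their last available (scheduled or unscheduled) tumor assessment", limited only to scans that showed no progression. For those who die without objective progression, "duration of confirmed response and duration of unconfirmed response will be censored on the date of death, regardless of cause". Early study discontinuation is censored at the last progression-free scan. The Part A1 SAP adds one further group: "Likewise, participants who have not discontinued early and do not have documented objective disease progression after a confirmed or unconfirmed response".
- **DOR sensitivity analysis**: clinical progression also counts as an event, and censoring moves to the date of last contact. In Part A this covers participants who discontinue early, complete or are ongoing; in Part A1 it covers early discontinuations only.

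Subsequent anti-cancer therapy appears nowhere in the DOR rules of either SAP. Section 4.3 (Part A) and Section 4.5 (Part A1) state that DOR uses all scheduled and unscheduled assessments, so no general rule supplies the cut-off. Both SAPs refer to a Derivation of Efficacy Endpoints document, version 0.6, for further detail on DOR.

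**The concern.** The three endpoints describe the same participant's course on UCB6114 monotherapy, and two of them stop at the next anti-cancer treatment. Followed as written, the third does not. A responder who stops UCB6114 without progression and starts something else stays under observation for DOR, so part of the reported duration may belong to the other treatment.

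The end rules also come apart. A response begins after first dose, so under common end rules DOR is shorter than PFS. Under the written rules the same participant can have a DOR longer than the censored PFS time, with nothing in the SAP to explain it.

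DOR is reported by treatment group with Kaplan-Meier quartiles and rates at 3, 6 and 9 months (Section 10.1.2 of both SAPs). If responders are few, one such participant can determine the estimate.

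**Working it through.** The plan gives no figure to reproduce. The check applies the SAP's own date formulas to one illustrative Part A participant.

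**Formulas** (Section 10.1.1): DOR = (end date − response start) + 1; PFS = (end date − first dose) + 1. First dose is Day 1.

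**Dates from the schedule** (28-day cycles, target scan on Day 22 of even cycles):
- Cycle 2 Day 22 = 28 + 22 = Day 50
- Cycle 4 Day 15 = 84 + 15 = Day 99
- Cycle 4 Day 22 = 84 + 22 = Day 106
- SFU visit, about 30 days after last dose = 99 + 30 = Day 129
- Final Visit, about 3 months (taken as 91 days) after last dose = 99 + 91 = Day 190

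**Assumed course**: PR on Day 50, confirmed on Day 106, last dose Day 99, new therapy Day 110, no objective or clinical progression before that.

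PFS, main and sensitivity: censored at the Day 106 scan, (106 − 1) + 1 = 106 days. This takes the therapy rule as overriding a later death, which the same-day provision implies.

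DOR if the PFS rule applied: censored at (106 − 50) + 1 = 57 days.

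DOR as written:

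| What ends DOR | Day | DOR | Status | Days past the Day 106 scan |
|---|---|---|---|---|
| Progression-free SFU scan, nothing later | 129 | 129 − 50 + 1 = 80 | censored | 23 |
| Progression on the new therapy | 162 | 162 − 50 + 1 = 113 | event | 56 |
| Death without progression | 170 | 170 − 50 + 1 = 121 | censored | 64 |
| Last contact at Final Visit (sensitivity analysis) | 190 | 190 − 50 + 1 = 141 | censored | 84 |

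Every row exceeds 57 days. The last three also exceed the PFS time of 106; the first does not.

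**When DOR exceeds PFS.** Let R be the day of first response, L the last scan before new therapy and E the DOR end date. DOR > PFS means E − R + 1 > L, that is E − L > R − 1. For a response at the first Part A scan (Cycle 2 Days 21 to 28, so Days 49 to 56), the gap must exceed 48 to 55 days, or about 7 to 8 weeks. At the Part A1 target of Day 57 it must exceed 56 days. Later first responses need a longer gap.

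**Direction of the Kaplan-Meier effect.**
- Add an assumed second responder with an event at 200 days. With the first responder's progression at 113 days, the curve as written falls to 1/2 at 113 and 0 at 200. Under the PFS rule the first responder is censored at 57, the only event is at 200, and the curve stays at 1 until then. The change raises the curve.
- If instead the first responder is censored at 80 days as written and the second progresses between 57 and 80 days, the curve as written falls to 1/2, because two are at risk. Under the PFS rule one is at risk and it falls to 0. The change lowers the curve.

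**The case against.** Four points on the other side carry weight.

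- **The derivation document.** Version 0.6 may contain a therapy rule for DOR, and it cannot be checked here. However, the SAP refers to the same document for PFS and still writes the PFS rule out. A detailed DOR censoring list without that rule reads as a different rule. If the document does contain one, the SAP text needs to match it.
- **A deliberate choice.** Following response through new therapy is a possible strategy. The SAP neither says so nor gives a reason, and it does the opposite for BOR and PFS.
- **Limited reach.** BOR closes at new therapy, so another treatment cannot make someone a responder; only the tail of DOR is open. A progression found well after the SFU visit would need an unscheduled scan, and the disease assessment on the survival pages is described only as listed. This stands for the progression row, but the death and last-contact rows need no scan.
- **Comparing unlike times.** A censored PFS time is only a lower bound, so a longer DOR is not an arithmetic contradiction. It shows that the two endpoints use different end rules.

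Two stronger readings are tempting but unsupported. A reader might infer that DOR is biased upward. The individual times are longer, but applying the PFS rule can turn an event into a censoring, and the working shows the curve moving either way.

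A reader might also infer that radiotherapy or surgery would escape PFS censoring, because BOR names both while the PFS text says therapy use is "identified via ongoing medical review of the concomitant medications together with the start dates of further anti-cancer therapy information recorded on the survival follow-up pages". The survival pages record any further antitumor treatment and its type, and nothing says that on-study cancer procedures are recorded only elsewhere. No mismatch of sources is shown.

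**Conclusion.** The point holds as an inconsistency in the written rules of both SAPs. BOR and PFS stop at subsequent anti-cancer therapy; the DOR text does not. DOR as written can therefore include time on another treatment. It is clearest in the Part A sensitivity analysis, where last contact alone can set the end date while the matching PFS sensitivity analysis keeps the therapy cut-off.

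In the illustration the difference is 23 to 84 days in one participant, and DOR overtakes the censored PFS time in three of the four cases. These figures rest on assumed dates and on a responder who starts new therapy without prior progression. How often that will happen cannot be told from the SAP.

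The consequence is moderate. Antitumor activity is exploratory, DOR is descriptive and analyzed only if the data allow, and the primary objective is safety. The correction is still worth making before database lock because it is cheap and the plan already derives the date it needs.

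**What to change.** In Section 10.1.1 of both SAPs, extend the PFS therapy rule to duration of confirmed and unconfirmed response and to their sensitivity analyses. Responders who start subsequent anti-cancer therapy without prior progression would be censored at the last tumor assessment before it starts. State that this takes precedence over censoring at death, at a later scan or at last contact.

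Carry over the same-day provision, so that progression documented on the start date remains an event. A scan on the start date should be handled as BOR already handles it; otherwise an unconfirmed response first seen that day would be censored before it began.

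Use one therapy-start date for BOR, PFS and DOR, and bring the derivation document into line. If following response through new therapy is intended, the SAP should say so and give the reason.

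The cost is a few sentences in each SAP and reuse of the PFS censoring date. The downside is more censored DOR times, so some quartiles and 3-, 6- and 9-month rates may become less precise or not estimable.

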10 EFFICACY ANALYSES

10.1 Antitumor activity

The analysis of antitumor activity is exploratory in Part A of this study.

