Overall survival (OS) will be calculated as the time in days from the date of first dose of study treatment to the date of death from any cause. Participants will be followed up to ascertain their survival status at the SFU visit (within 30 days after their last dose of study treatment) and at the Final Visit (3 months after their last dose of study treatment); they will not be followed up beyond this timepoint.

The following calculation will be performed:

$$OS = (Date\ of\ Death - Date\ of\ First\ Dose\ of\ Study\ Treatment) + 1$$

For participants who discontinue early from Part A of the study or who discontinue study treatment due to disease progression but continue in the study, who complete the Part A, or who are ongoing in the study at a data cut-off for Part A, but are not known to have died, OS will be censored on the date of their last contact.

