Duration of confirmed response, duration of unconfirmed response and PFS will be listed and summarized descriptively using Kaplan-Meier estimation. These summaries will be repeated for the sensitivity analyses of these endpoints (defined in Section 10.1.1 above) and will include the number and percentage of participants with the event, the number and percentage of participants censored, minimum and maximum values and Kaplan-Meier estimates of the 25th percentile, median, 75th percentile and corresponding 95% CIs calculated using Greenwood's formula. In addition, DOR and PFS rates at specific timepoints (3 months, 6 months, 9 months) will be derived from the Kaplan-Meier estimation and presented together with associated 95% CIs.

Kaplan-Meier curves will be presented for duration of confirmed response, duration of unconfirmed response and PFS, and for the associated sensitivity analyses. Treatment groups will be overlaid on each plot.

Survival status collected on the eCRF at the SFU visit and at the Final Visit will be listed for each participant by treatment group. This listing will include the participant's survival status,

date and cause of death, whether an autopsy was performed and date of autopsy, whether the participant had received any further antitumor treatment after the last dose of study treatment and the type of treatment, and whether the participant's disease had been assessed since the end of study treatment including method of assessment and the overall response.

Overall survival times will be listed and summarized descriptively using Kaplan-Meier estimation. Note that since participants are only followed up for survival until the Final Visit in Part A of the study, a summary of OS may not be meaningful (i.e. if no participants die then OS cannot be assessed).

Additional exploratory analyses of selected antitumor activity endpoints may be performed based on subgroups of participants in the SS.

Additionally, the relationship of the antitumor activity variables with key PK parameters may be explored but this will be reported separately.

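### The last-contact date that censors OS may be set by the premature study termination date even when that date records no contact, so OS can be biased upward

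*SAP*

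**What the plan says.** Section 10.1.1 of the Part A SAP defines OS as "the time in days from the date of first dose of study treatment to the date of death from any cause". For participants who leave early, stop treatment for progression, complete the part or are ongoing at a cut-off, the rule is: "but are not known to have died, OS will be censored on the date of their last contact".

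The only definition of that date is in the DOR text of the same section: "Date of last contact will be the latest of the dates of premature study termination and of last contact recorded" on the study termination page. The list continues with date of death, last dose, all visits, adverse event start and end dates, and the contact dates on the two survival follow-up forms.

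The same date serves two other analyses:
- **Sensitivity PFS:** "Last contact date (as defined above for DOR) will be used for the censoring of participants still alive with no reported disease progression".
- **Sensitivity DOR:** in Part A it applies to participants who leave early, complete the part or are ongoing; in Part A1 it is stated only for those who leave early.

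Section 10.1.1 of the Part A1 SAP repeats the definition and the OS rule. In both parts survival is checked at the Safety Follow-up visit and at the Final Visit, three months after the last dose, and "they will not be followed up beyond this timepoint".

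**The concern.** Censoring at last contact is valid for OS because the participant was known to be alive up to that day. The termination date is the one entry in the list that need not carry this information. Where it falls after the last real contact, the participant stays in the risk set over a period when a death might not be recorded. The denominators of the Kaplan-Meier factors are then too large and the curve too high. The SAP foresees the participants concerned: its definition of the end of Part A (section 3.2.2) provides for people who leave without attending the Safety Follow-up visit. A cohort with more loss to follow-up would be flattered more than one with less.

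**Working it through.** **1. When the termination date matters.** Let *C* be the latest of all other listed dates and *T* the premature termination date. The rule gives max(*C*, *T*).
- *T* ≤ *C*: the result is *C*, and the termination date does nothing.
- *T* > *C*, and *T* itself records a contact not entered elsewhere: using *T* is right.
- *T* > *C*, and *T* records no contact: *T* − *C* days of undocumented vital status are added.

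The SAP does not separate the second case from the third. Date of death in the list is harmless for OS, since a known death is an event.

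**2. Hand example (invented data, cohort of 6).** Deaths occur on Days 60 and 100. One participant was last known alive on Day 50 and terminated on Day 80. Three are censored on Day 133. Survival at Day 100 is the product of (1 − 1/number at risk):
- Censored on Day 50: (1 − 1/5) × (1 − 1/4) = 0.800 × 0.750 = 0.600.
- Censored on Day 80: (1 − 1/6) × (1 − 1/4) = 0.833 × 0.750 = 0.625.

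One participant moves the estimate by 2.5 percentage points.

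**3. Expected size.** The SAPs state no figure that depends on this rule, so there is none to reproduce. From the SAP: with the planned two cycles in Part A, the last dose is Cycle 2 Day 15, which is Day 28 + 15 = 43. Three months of follow-up, taken as 90 days, ends on Day 133. Assumed, because the SAPs do not give them: exponential OS with median *m* of 120 or 240 days; 5%, 10% or 20% lost, with last contact uniform over Days 1 to 133; a gap of 0, 14, 30 or 90 days to the termination date; deaths in the gap undetected.

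True survival at Day 120 is exp(−ln 2 × 120/*m*): 0.500 for *m* = 120 and 0.707 for *m* = 240. With *O*(*t*) the share truly under observation and *G*(*t*) the share carried through a gap, the Kaplan-Meier hazard becomes λ*O*/(*O* + *G*) instead of λ = ln 2/*m*. It is too low whenever *G* > 0.

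Error in Kaplan-Meier survival at Day 120, in percentage points, from simulation with 400,000 participants per scenario (*m* = 120 / *m* = 240):

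| Lost | 14-day gap | 30-day gap | 90-day gap |
|---|---|---|---|
| 5% | +0.1 / +0.1 | +0.4 / +0.3 | +0.9 / +0.6 |
| 10% | +0.4 / +0.2 | +0.8 / +0.6 | +1.8 / +1.1 |
| 20% | +0.6 / +0.5 | +1.6 / +1.1 | +3.7 / +2.5 |

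With a gap of 0 the error at Day 120 is at most 0.1 points either way, so censoring at the date last known alive is unbiased. Integrating the hazard formula numerically reproduces every cell to within about 0.2 points. If follow-up is extended to Day 365, the error at Days 91, 182 and 273 is at most about +1.8 points.

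These figures concern survival. The effect on the sensitivity PFS and DOR has the same direction but was not quantified.

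**The case against.** The strongest reply is that neither SAP says the termination date is administrative or later than the last contact. The definition shows only that the page holds two dates. For someone who withdraws at a visit or by telephone they may coincide, and then the entry is redundant. This stands: the bias is possible, not established. A reader might infer that every participant lost to follow-up is carried alive to a closing date and that OS is therefore biased; the text does not support that.

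Nor does the rule contradict the SAP's own OS censoring. Last contact is a defined term, and the OS rule uses it. The fault is one component of the definition.

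A reader might also reach larger figures. With 8 participants, 25% lost after last contact on Days 20 to 90 and all carried to Day 134, mean Kaplan-Meier survival at Day 120 rises from 0.44 to 0.50 (median OS 100 days) or from 0.73 to 0.76 (250 days). Every gap is then 44 to 114 days and passes the reading point. That is close to a worst case on inputs the SAPs do not give, and should not stand as the typical effect.

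The Derivation of Efficacy Endpoints document, which is not at hand, might restrict the date. The Part A1 SAP cites it for OS; the Part A SAP cites it for DOR and PFS but not in its OS text. Both SAPs still state the rule without restriction.

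The stakes are low. The Part A SAP says: "The analysis of antitumor activity is exploratory in Part A of this study", and Part A1 has the same status. Both warn that "a summary of OS may not be meaningful". Fixed-time rates are planned for DOR and PFS, not for OS. Dose escalation in Part A rests on safety and tolerability with PK, PD and ADA data where available. The main PFS analysis, and the main DOR analysis apart from deaths, censor at the last tumor assessment and do not use this date. All of this limits the consequence but does not make the entry right.

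**Conclusion.** The point holds as a defect of definition with a conditional consequence. Both SAPs let the premature termination date set the last-contact date without requiring that it document a contact. It acts only when it is later than every other listed date. If it then reflects no contact and deaths in the gap go undetected, Kaplan-Meier OS can be overstated, and so can the sensitivity PFS and DOR. On the assumptions above, the overstatement of survival at Day 120 is about +0.1 to +3.7 percentage points; in a cohort of six, a single participant can move the curve by a few points. If the gap is zero, or the death becomes known, there is no bias. Taking the latest of several genuine contact dates is sound. This is a modest correction to an exploratory, descriptive analysis, and no trial decision in the SAPs is tied to OS.

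**What to change.** In section 10.1.1 of both SAPs, replace the last-contact definition with the last date on which the participant was documented alive: the latest of last dose, attended visits, the last-contact field, survival follow-up contacts and other dates that evidence contact. Count the premature termination date only when it records an actual contact, for example consent withdrawn in person. Cross-refer to this definition from the OS paragraph, and use it for the sensitivity PFS and DOR wherever last contact is cited. Check that the Derivation of Efficacy Endpoints document says the same.

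The cost is one or two sentences and one derivation per SAP, using dates already collected. The downside is that some censored times become shorter.
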